6. MILESTONES

Milestone	Planned Date
Start of data collection	December 2019
End of data collection	The end of data collection is determined by the sufficient number of patients enrolled and pertinent data entered in eDC.
Registration in the EU PAS register	October 2019
Interim report	According to patients data availability the possibility to perform an Interim Analysis by the end of 2020 will be considered.
Final report of study results	2021

7. RATIONALE AND BACKGROUND

Patients with non-small-cell lung cancer (NSCLC) represent a heterogeneous population; however, increased understanding of the molecular pathogenesis of the disease has allowed for new treatments using molecularly targeted anti-cancer agents. Currently, the most established target is the epidermal growth factor receptor (EGFR) ([P15-00464](#)). Four EGFR tyrosine kinase inhibitors (TKIs; erlotinib, gefitinib, afatinib and osimertinib) are currently globally available for the management of NSCLC.

The two most common EGFR mutations (in-frame deletion in Exon 19 (Del19) and Point mutation in Exon 21 (L858R)) account for >85% of all mutation-positive NSCLC cases and are known to confer sensitivity to EGFR TKIs ([P14-02931](#)), whereas the efficacy on uncommon mutation is still debated.

Although several EGFR TKIs are available for the treatment of EGFR mutation-positive NSCLC, the development of acquired resistance is inevitable. It is therefore beneficial to consider the optimal sequence of EGFR TKIs in order to maximize their clinical benefit ([P18-01208](#))

There are limited real world data with regard to EGFR mutated, advanced NSCLC who are EGFR TKI naïve therefore the aim of this study will be to collect more information on the benefit of individual EGFR-TKIs treatment for the uncommon mutations and the overall benefit for the sequential EGFR TKI treatment with afatinib and osimertinib for the common EGFR mutations. These findings will allow for evidence-based therapy decision.

[figure not shown]
This global Real-World non-interventional, multi-country, multi-centre study will be collecting pre-existing data from medical records for the patient population: EGFR mutated, advanced NSCLC who are EGFR TKI naïve, in the following two cohorts:

1- Uncommon mutation cohort

Patient with uncommon EGFR mutations who started EGFR TKI (afatinib, gefitinib, erlotinib, osimertinib) in first or second line and with treatment initiated at least 12 months prior to data entry. About 250 eligible patients are planned to be enrolled.

2- Sequencing cohort

Patient with common EGFR mutations who started osimertinib in second line for acquired T790M at least 10 months prior to data entry. As first-line patients underwent afatinib. About 200 eligible patients are planned to be enrolled.

*Patient must have been treated with EGFR-TKI in either 1st or 2nd line, 2nd line treatment after 1st line EGFR-TKI is not mandatory.

Figure 7:1 Overview of the two cohorts

7.1 UNCOMMON MUTATION COHORT

In a retrospective analysis of 1632 patients with stage IIIB-IV NSCLC, uncommon mutations occurred in ~16% of EGFRm+ NSCLC cases: exon 20 insertions (9%), uncommon mutations with Del19 or L858R complex mutations (30%) [Del19 + 18G721D; Del19 + 19L732P; Del19+ 20L792P; Del19+ 20S768I + 20V774M; Del19 + 21L858R + 21K860I; 21L858R + 18E709X; 21L858R + 20S768I; 21L858R + 20V786E; 21L858R + 20T790M; 21L858R + 20 insertion; 21L858R + 21L833V1 21L858R + 21K860I; 21L858R + 18G719X +20 insertion]; uncommon mutation alone or in combination with other uncommon mutations (61%) [18I715V; 18K716E; 18V717G; 18G719X; 19L747P; 19 insertion; 20A763_Y764 insFQEAE; 20S768I; 20G779F; 21L861Q; 18G719X + 21L861Q; 18E709X + 18G719X; 18G719X + 20S768I; 20T790M + 21L861Q; 21M825L +21R831C; 18V703L + 18L707W +18G719X; 18E709X + 18T710S + 18G719X; 19V742F + 19A743 V + 20H773R] ([P17-07438](#)).

Recent improvements in detection methods have indicated that 'uncommon' EGFR mutations are more prevalent than previously thought. According to the catalogue of somatic mutations in cancer (COSMIC) database, in 2016, 594 types of EGFR mutation had been reported ([P16-09907](#)). Categories of uncommon mutation include insertions in exon 19 (Ins19; 0.6% of all EGFR mutations) or 20 (Ins20; ~6%), as well as point mutations in exon 18 at position G719 (G719X; ~3%), exon 21 L861Q mutations (~1%) and exon 20 S768I mutations (~1% of EGFR mutations) ([P16-09907](#)). In addition, it is becoming increasingly clear that some patients with EGFR mutation-positive NSCLC have tumors that harbor more than one type of EGFR mutation, predominantly in cis, in other words, within the same EGFR allele (so-called 'compound' mutations).([P19-02454](#), [P18-10855](#)).

Afatinib is an irreversible ErbB family blocker and the first marketing approval of afatinib was granted on 12 Jul 2013 in the US (trade name Gilotrif®) for the indication of first-line

treatment of patients with metastatic non-small cell lung cancer (NSCLC) whose tumours have EGFR exon 19 deletions or exon 21 (L858R) substitution mutations as detected by an Food and Drug Administration (FDA)-approved test. It was approved in the European Union (EU) on 25 Sep 2013 (trade name Giotrif®) as monotherapy indicated for the treatment of EGFR TKI-naïve adult patients with locally advanced or metastatic NSCLC with activating EGFR mutation(s). On January 12, 2018, FDA granted approval to afatinib for a broadened indication in first-line treatment of patients with metastatic NSCLC whose tumours have non-resistant EGFR mutations as detected by an FDA-approved test ([P19-04170](#)). Approval was based on demonstration of durable responses in a subset of 32 afatinib-treated patients with metastatic NSCLC harbouring non-resistant EGFR mutations (S768I, L861Q, and/or G719X) other than exon 19 deletions or exon 21 L858R substitutions enrolled in one of three clinical trials (LUX-Lung 2 [NCT00525148], LUX-Lung 3 [NCT00949650], and LUX-Lung 6 [NCT01121393]). The confirmed overall response rate, as assessed by independent radiology review, was 66% (95% confidence interval 47, 81). Among the 21 responders, the proportion of patients with response duration of ≥ 12 months was 52% and the proportion with response durations of ≥ 18 months was 33%. Clinical benefit was lower in patients with de-novo Thr790Met and exon 20 insertion mutations. ([P15-05932](#))

Gefitinib (IRESSA®) and erlotinib (Tarceva®) are first generation EGFR-TKIs and approved by EMA as monotherapy for the treatment of adult patients with locally advanced or metastatic non-small cell lung cancer (NSCLC) with activating mutations of EGFR-TK. FDA label is restricted to common mutations (Del19 and L858R).

Anecdotal data from erlotinib/gefitinib trials show variable and mainly limited responses to EGFR TKIs in a multitude of other EGFR mutations, eg, in Exons 18-21 or a combination of ≥ 2 EGFR mutations ([P16-09907](#)) Post-hoc analyses from the NEJ002 study comparing gefitinib with chemotherapy showed that patients with uncommon EGFR mutations had a significantly shorter OS (11.9 versus 29.3 months; $p < 0.001$). By contrast, OS was similar for uncommon mutations and common mutations in the CarboPac group ($n = 111$; 22.8 versus 28 months; $p = 0.358$) ([R19-1656](#)).

Osimertinib (Tagrisso®) is approved by EMA for the first-line treatment of adult patients with locally advanced or metastatic NSCLC with activating EGFR mutations, and for the treatment of adult patients with locally advanced or metastatic EGFR T790M mutation-positive NSCLC. The FDA label restricts osimertinib in first line to common EGFR mutations. Data from a Korean phase 2 IIS showed benefit for osimertinib in 36 patients with G719A/C/D/S/X L861Q, S768I, and four other mutations. The overall response rate was 50.0% (95% CI 32.8-67.2) and DCR was 88.9% (95% CI 78.1-99.7) ([R19-1672](#)).

Given the robust evidence for osimertinib in acquired T790M from randomized controlled trial (AURA-3) ([P17-01960](#)), no further data on EGFR-TKI effectiveness in this indication is needed.

Dacomitinib (Vizimpro) is not approved outside common mutations and will therefore not be analysed.

The heterogeneity of EGFR mutations in EGFR mutation-positive NSCLC has potential clinical implications because different EGFR-targeted TKIs can have different activities against specific mutations. Therefore, treatment with EGFR TKIs that have limited efficacy against certain mutations may drive the clonal expansion of those insensitive mutations. A recent preclinical study assessed the activity of different EGFR-directed TKIs against

uncommon EGFR variants of unknown significance. By utilizing a high-throughput functional assay in Ba/F3 cells, Kohsaka et al. evaluated the sensitivity of over a hundred different variants of unknown significance, including compound mutations ([P18-10855](#)). Interestingly, afatinib showed activity against almost all mutations tested and, in many cases, was more potent than erlotinib and gefitinib. Afatinib also showed a broader spectrum of activity against uncommon EGFR variants compared with osimertinib, although, as expected, afatinib was less effective against T790M than osimertinib ([P18-10855](#)).

Various methodologies with different sensitivities can be used for detection of EGFR mutation. Little is known about the sensitivity for uncommon or compound mutation. Thus, it is of interest to learn more about the methods that have been used to identify patients harbouring tumours with uncommon mutations ([R19-1655](#)).

In summary, there seems to be only limited efficacy of first generation EGFR-TKI, and limited data on osimertinib who has furthermore only recently been approved for first line. In many countries, the labels for these drugs are restricted to common mutations, whereas afatinib's efficacy has been confirmed in clinical trials and being acknowledged by regulatory authorities. Given this, the uncommon mutation cohort should enrol at least 50% of patients who were treated with afatinib. Furthermore, as patients with EGFR mutations should be treated in first-line as recommended by NCCN and ESMO guidelines, at least 50% of enrolled patients should have been treated in first line.

Thus, more information on the benefit of individual EGFR-TKIs on individual uncommon mutations is needed to allow for evidence-based therapy decision. Furthermore, more information is needed on outcome with other systemic therapy and OS.

7.2 SEQUENCING COHORT

Metastatic epidermal growth factor receptor (EGFR)-mutant lung cancers are sensitive to first- and second-generation EGFR tyrosine kinase inhibitors (TKIs) gefitinib, erlotinib and afatinib ([P14-03814](#)).

Afatinib is an irreversible ErbB family blocker and the first marketing approval of afatinib was granted on 12 Jul 2013 in the US (trade name Gilotrif®) for the indication of first-line treatment of patients with metastatic non-small cell lung cancer (NSCLC) whose tumours have EGFR exon 19 deletions or exon 21 (L858R) substitution mutations as detected by an Food and Drug Administration (FDA)-approved test. It was approved in the European Union (EU) on 25 Sep 2013 (trade name Giotrif®) as monotherapy indicated for the treatment of EGFR TKI-naïve adult patients with locally advanced or metastatic NSCLC with activating EGFR mutation(s). In total, marketing authorisation for Gi(l)otrif® has been granted in more than 80 other countries world-wide as of today ([c01802941-10](#)).

On the clinical trials LUX-Lung 3 ([P13-07382](#)), LUX-Lung 6 ([P14-00758](#)) and LUX-Lung 7 ([P16-04350](#)), afatinib (Gi(l)otrif®) showed a median progression-free survival (PFS) of 11.1, 11.1 and 13.6 months, respectively, for patients with EGFR common mutations (Del19 and L858R) treatment-naïve. Time to treatment failure in LUX-Lung 7 was 13.7 months.

Eventually, resistance develops for most patients and the most common mechanism of resistance to EGFR TKIs (>50%) is the emergence of a second-site EGFR-mutation, the T790M ([R15-6101](#), [P09-09950](#)).

Explorative analysis of LUX-Lung 7 showed a median overall survival of not being reached for patients who started with afatinib (Gi(l)otrif®) and received subsequently osimertinib or olmutinib (follow-up period of 42.6 months) indicating a long-time benefit from this sequence([P19-03125](#)).

Osimertinib, a third generation EGFR TKI, was approved for patients whose tumours have developed the EGFR T790M mutation by several countries. The first marketing approval of osimertinib was granted on 13 Nov 2015 in the US ([R16-5838](#)). The EU and Japan also gave a similar approval on 03 Feb 2016 and 29 Mar 2016 separately ([P16-15191](#), [P16-15190](#)).

In addition, osimertinib has been studied in the first-line treatment in the FLAURA trial. Osimertinib significantly prolonged PFS compared to first generation TKIs (erlotinib or gefitinib). Median PFS by independent review was 17.7 months in patients with common mutations ([R18-0130](#)). Overall survival data are still immature and so far, only 29% of the patients treated first-line with osimertinib received a subsequent therapy. Furthermore, as more than 60% have no putative resistance mechanism and even those identified are not druggable with approved targeted therapies, the best sequencing strategy is still under discussion.

A recent global real-world study (GioTag) recruited from December 2017 to May 2018 and provided insights into the outcomes of patients treated with the sequence afatinib followed by osimertinib. Time on treatment for the sequence was 27.6 months and 2 year survival rate being 79% ([P18-09968](#)). This study enrolled mainly Caucasian patients (59%) and 63% of the patients came from USA, although incidence of EGFR mutated NSCLC is much higher in Asian countries ([R19-1657](#)). Study timelines and availability of drugs led to limited enrolment of long-term responders (10-12% of patients treated with afatinib are for 3 years and longer on drug) ([P19-03124](#)) and maturity of time to treatment failure was 52% and 31% for OS. Thus, more data from Asian patients and with meanwhile longer availability of both drugs will provide data that are more robust with an increased maturity. At least 60% of enrolled patients should have Asian ethnicity.

Various methodologies with different sensitivities can be used for T790M detection. Recently, it could be shown that in patients who progressed under treatment with an EGFR TKI, the T790M positivity rate was 66% using ddPCR, but only 24% using Cobas ([P19-03686](#)). Thus, it is of interest to learn more about the methods that have been used to identify patients qualifying for the sequence afatinib followed by osimertinib.

Investigating in this real-world data (RWD) study the time from start of first-line afatinib (Gi(l)otrif®) until the end of second-line osimertinib in this study provides insights on treatment sequence that can inform on the most beneficial treatment sequence for the patients.

8. RESEARCH QUESTION AND OBJECTIVES

Data from real-world setting would inform on the beneficial treatments in patients diagnosed with advanced NSCLC harbouring uncommon EGFR mutations and on the treatment sequence in patients diagnosed with advanced common EGFR mutation NSCLC.

Primary objective:

For both cohorts the study aims to describe the time on treatment until its end or death.

More specifically, this will be evaluated for each cohort as follows:

Uncommon mutation cohort:

To determine the time on treatment of EGFR-TKIs as first or second line therapy in NSCLC with uncommon Epidermal Growth Factor Receptor (EGFR) mutations. Time on treatment is defined from the start of EGFR-TKI until the end of EGFR-TKI treatment or death date by any cause.

Sequencing Cohort:

To determine the time on treatment of afatinib (Gi(I)otrif®) as first-line therapy in patients with EGFR mutation-positive NSCLC followed by osimertinib in case the T790M resistance mutation was developed. Time on treatment is defined from the start of the first-line treatment until the end of the second-line treatment or death date by any cause.

Secondary objectives:

To determine the overall response rate, and overall survival. To describe the methodology and material (liquid vs tissue) used for detection of uncommon/T790M mutation. Uncommon mutation cohort only: To determine the time on treatment until the end of the second-line treatment.

9. RESEARCH METHODS

9.1 STUDY DESIGN

This is a non-interventional, multi-country, multi-centre cohort study based on existing data from medical records (paper or electronic) or electronic health records of patients with advanced NSCLC harbouring EGFR mutations and treated with an EGFR-TKI.

In total, at least 200 eligible patients in the sequencing cohort and approximately 250 eligible patients in the uncommon cohort.

Key study outcome:

Time on treatment with EGFR-TKI(s)

The study will involve secondary use of data.

Since the collected data include also genetic data, the appropriate strategies to ensure data protection (such as strong authentication) will be implemented in the eCRF employed for data collection.

9.2 SETTING

It is planned that around 65 study centres in up to 11 countries will be participating in this non-interventional study and at least 200 consecutive eligible patients in the sequencing cohort and approximately 250 patients in the uncommon cohort from up to 80 sites will be enrolled to the study. Data extraction from local data bases might be used when possible. Every patient who fulfils inclusion and exclusion criteria and agree to participate in the study (if a written informed consent is required for this NIS by local regulation and legal requirement) will be selected until the required sample size is achieved. Deceased patients should be enrolled whenever possible. This has to be discussed with the local authorities. Investigators who fail to enrol at least one patient in the first 8 weeks of the study may be excluded from further participation. If enrolment is delayed additional countries and centres may be recruited.

To avoid differential centre influence on study results, permission to enrol more than 15 patients per site and cohorts must be obtained from the CTL.

Recruiting of patients for this study is competitive, i.e., recruitment will stop at all centres when it is determined that a sufficient number of patients have been enrolled. Investigators will be notified when the appropriate number of patients has been enrolled and recruitment is complete, and will not be allowed to recruit additional patients for this study.

9.2.1 Selection of study population

Site selection:

Sites with access to paper/electronic medical charts/electronic health record (EHR) that have treated patients according to inclusion criteria:

1. Adult patients
2. diagnosed with Epidermal Growth Factor Receptor Tyrosine Kinase Inhibitor (EGFR-TKI) naïve advanced EGFR mutated non-small cell lung cancer (NSCLC),
3. treated for Epidermal Growth Factor Receptor (EGFR) mutated NSCLC within regular clinical practice.
4. Informed and privacy consent signature must be obtained depending on local regulations.

More specific inclusion criteria for each cohort are the following:

Uncommon mutation cohort:

5. Patients harbouring uncommon or compound EGFR mutations
6. Patients who started with either afatinib (Gi(I)otrif[®]), gefitinib (Iressa), erlotinib (Tarceva), or osimertinib (Tagrisso) in the first- or second-line setting within regular clinical practice
7. Patients must have started EGFR-TKI treatment at least 12 months prior to data entry.

Sequencing cohort:

5. Patients with common EGFR mutations (Del19, L858R)
6. Patients were treated with afatinib (Gi(I)otrif[®]) in the first-line setting and for acquired T790M mutation with osimertinib in the second line;
7. Patients must have started osimertinib treatment at least 10 months prior to data entry. Patients treated with osimertinib within an early access program/ compassionate use program (EAP/CUP) are allowed

Main exclusion criteria:

1. Patients treated for EGFR mutated NSCLC within a clinical trial or participated in GioTag study.
2. Patients with active brain metastases at start of EGFR-TKI therapy (independent of treatment line)
3. For uncommon mutation cohort: Patients treated with osimertinib with no further uncommon mutation than acquired T790M

Deceased patients fulfilling the eligibility criteria should be enrolled whenever possible.

Uncommon mutation cohort: Patients treated with EGFR-TKI in interventional trials are excluded to ensure the non-interventional setting of this study. The threshold of start of treatment at least 12 months respectively prior to data entry was chosen based on the median PFS reported for patients being treated with afatinib in the LUX-Lung 2, -3, -and 6 trials ([P15-05932](#)) to avoid early censoring and enable collection of mature data on adverse drug

reactions (ADRs) and treatment duration. All patients fulfilling inclusion and exclusion criteria from a site will be entered to avoid bias.

Sequencing cohort: Patients treated with afatinib (Gi(l)otrif®) and/or osimertinib in interventional trials are excluded to ensure the non-interventional setting of this study. Real-world studies such as ASTRIS are not affected by this exclusion ([R17-0754](#)). The threshold of start of osimertinib at least 10 months prior to data entry was chosen based on the median PFS result of AURA-3 ([P17-01960](#)) to avoid early censoring and enable collection of mature data on treatment duration. All patients fulfilling inclusion and exclusion criteria from a site will be entered to avoid bias.

A log of all patients included into the study will be maintained in the ISF at the investigational site.

BI reserves the right to discontinue the study overall or at a particular study site at any time for the following reasons:

1. Failure to meet expected enrolment goals overall or at a particular study site.
2. Violation of Good Clinical Practice (GCP) (as applicable), the Study Protocol, or the contract by a study site or investigator, disturbing the appropriate conduct of the study.

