1 STATISTICAL ANALYSIS PLAN OBJECTIVES

The UPSWING study is an observational (Real-World, non-interventional), multi-country, multi-center, retrospective study (based on existing data from medical records or electronic health records) on two cohorts of adult patients diagnosed with EGFR-TKI naïve advanced EGFR-mutated NSCLC, treated for EGFR mutated NSCLC within regular clinical practice. The two cohorts are the following:

- *Uncommon Mutation cohort*: patients who started at least 12 months prior to end of observation an EGFR-TKI treatment (ie. either afatinib, gefitinib, erlotinib, or osimertinib) in the first- or second-line setting within regular clinical practice in presence of uncommon or compound EGFR mutations. Patients treated with EGFR-TKI in interventional trials are excluded (to ensure the non-interventional setting of this study). Also patients treated with osimertinib with no further uncommon mutation than acquired T790M cannot be enrolled.
- *Sequencing cohort*: patients who were treated with first-line afatinib in presence of common EGFR mutations (ie. Del19 and/or L858R) and subsequently, after having acquired T790M mutation, with second-line osimertinib (which shall have been started at least 10 months prior to end of observation) within regular clinical practice or within an Early Access Program (EAP) / Compassionate Use Program (CUP). Patients who participated in GioTag study shall be excluded, as well as patients treated with afatinib and/or osimertinib in interventional trials (to ensure the non-interventional setting of this study).

For both cohorts, patients with active brain metastases at start of EGFR-TKI cannot be enrolled.

At least 200 eligible consecutive patients are planned to be enrolled for each cohort. Beside alive patients, also deceased and untraceable patients can be enrolled, in order to avoid selection bias.

It is planned that around 65 study centres in up to 11 countries will be participating.

The following documents were considered in order to write this Statistical Analysis Plan:

- the Study Protocol (version 1.0, 23 July 2019);
- the electronic case report form v. 1.5.3, 05/02/2020;
- the minutes of the customer meeting held on 12th November 2019;
- the slide kit of the Data Analysis Strategic Meeting on 21st January 2020;
- the email correspondence with the Sponsor until 27/11/2020,
- the slide kit and minutes of the conference call with Sponsor held on 17th June 2020,

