(*) this means that if the start date of the index EGFR-TKI therapy is 9.49 months before date of data collection, the patient violates this criterion. This tolerance window has been agreed with the Sponsor during the Data Analysis Strategic Meeting, and will not be further discussed. Only in case exact day is not known and this makes the evaluation critical with the respect to the tolerance window, then case-by-case discussion will be done with the Sponsor.

Criterion 8 (UNCOMMON MUTATION COHORT). Patient not treated for EGFR mutated NSCLC within a clinical trial

- “Cohort” [PI. PI_coh_ty] = “Uncommon Mutation cohort” AND
- “1. Patient treated for EGFR mutated NSCLC within a clinical trial” in the ELIGIBILITY CRITERIA form [EC. EC_EC_1_umc] = “No” AND
- “1. Patient treated for EGFR mutated NSCLC within a clinical trial” in the PROTOCOL DEVIATION FORM [PDF. PDF_EC1_umc] is not flagged

Criterion 8 (SEQUENCING COHORT). Patient not treated for EGFR mutated NSCLC within a clinical trial nor participated in GioTag study

- “Cohort” [PI. PI_coh_ty] = “Sequencing cohort” AND
- “1. Patient treated for EGFR mutated NSCLC within a clinical trial or participated in GioTag study” in the ELIGIBILITY CRITERIA form [EC. EC_EC_1_sc] = “No” AND
- “1. Patient treated for EGFR mutated NSCLC within a clinical trial or participated in GioTag study” in the PROTOCOL DEVIATION FORM [PDF. PDF_EC1_sc] is not flagged

Patients treated with osimertinib within an early access program/compassionate use program (EAP/CUP) are allowed.

Criterion 9. Patient without active brain metastases at start of EGFR-TKI therapy (independent of treatment line)

- “2. Patient with active brain metastases at start of EGFR-TKI therapy (independent of treatment line)” in the ELIGIBILITY CRITERIA form [[EC. EC_EC_2](#)] = “No” AND
- “2. Patient with active brain metastases at start of EGFR-TKI therapy (independent of treatment line)” in the PROTOCOL DEVIATION FORM [[PDF. PDF_EC2](#)] is not flagged

Criterion 10 (UNCOMMON MUTATION COHORT only). Patient not treated with osimertinib without further uncommon mutations than acquired T790M

- “Cohort” [[PI. PI_coh_ty](#)] = “Uncommon Mutation cohort” AND
- “3. Patient treated with osimertinib with no further uncommon mutation than acquired T790M” in the ELIGIBILITY CRITERIA form [[EC. EC_EC_3_umc](#)] = “No” AND

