- patients with “Presence of any metastases?” **[CCPE. CCPE_met_YN]** = “UNK” will be classified as “UNK”.

Sites of metastases at second-line treatment start

The same algorithm will be applied considering the **[Second-line treatment period]** time period, considering only patients with Number of NSCLC treatment lines (as defined previously) >1.

Sites of metastases at index EGFR-TKI therapy start

The same algorithm will be applied considering the time period (ie. either **[First-line treatment period]** or **[Second-line treatment period]**) corresponding to the index EGFR-TKI therapy (as defined before).

Patients with presence of brain metastases at start of EGFR therapy (either at first- or second-line)

They will be those patients having:

- [First-line treatment period / CCPE. CCPE_met_site_3]** “Brain metastases” AND with first-line treatment corresponding to an EGFR-TKI

OR

- [Second-line treatment period / CCPE. CCPE_met_site_3]** “Brain metastases” AND with second-line treatment corresponding to an EGFR-TKI.

Changes in metastatic sites at start of osimertinib from start of afatinib

Considering patients of the SEQUENCING COHORT with known presence/absence of metastases both at afatinib start and at osimertinib start (ie. those with **[First-line treatment period / CCPE. CCPE_met_YN]** = (“Yes” OR “No”) AND **[Second-line treatment period / CCPE. CCPE_met_YN]** = (“Yes” OR “No”)), the following algorithms will be computed considering separately all the possible sites of metastases listed in field **[CCPE. CCPE_met_site, CCPE_met_site_sp]**:

- Patients with new metastatic sites:** considering all patients with no metastases in a specific site at **[First-line treatment period]** as denominator, it will be determined the absolute number and relative frequency of patients who have metastasis at the specific site at **[Second-line treatment period]**
- Patients with resolved metastases:** considering all patients with presence of metastases in a specific site at **[First-line treatment period]** as denominator, it will be determined the absolute number and relative frequency of patients who do not have metastases at the specific site at **[Second-line treatment period]**

Changes in metastatic sites at start of second-line treatment from start of first-line treatment

See previous algorithm, which will be applied for UNCOMMON MUTATION COHORT.

EGFR mutational status at first-line treatment start

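### In the uncommon mutation cohort, exclusions 1 and 2 are not tied to the start of the index EGFR-TKI, so patients can be removed for events that follow the primary endpoint

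*Protocol*

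**What the plan says.** **Exclusion 2.** The list in Protocol 9.2.1 reads "Patients with active brain metastases at start of EGFR-TKI therapy (independent of treatment line"). SAP 2.1, Criterion 9, mirrors it: "Patient without active brain metastases at start of EGFR-TKI therapy (independent of treatment line"). Criterion 9 is met by a No in the eligibility form and no flag in the deviation form; no date is compared. The Protocol abstract and SAP chapter 1 leave out the parenthesis; the latter says only that "patients with active brain metastases at start of EGFR-TKI cannot be enrolled".

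**Exclusion 1.** The list in Protocol 9.2.1 excludes "Patients treated for EGFR mutated NSCLC within a clinical trial or participated in GioTag study". SAP Criterion 8 for the uncommon cohort is "Patient not treated for EGFR mutated NSCLC within a clinical trial", again without a date or a drug. The rationale is narrower. For the uncommon cohort, Protocol 9.2.1 says "Patients treated with EGFR-TKI in interventional trials are excluded to ensure the non-interventional setting of this study", and SAP chapter 1 says the same. For the sequencing cohort, both documents name only afatinib and/or osimertinib given in interventional trials.

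**Index and time zero.** Under SAP chapter 3, the index in the uncommon cohort is the first-line EGFR-TKI whenever it qualifies, and the second line only otherwise. A patient may have an EGFR-TKI in both lines. Time on treatment and OS run from the index start. TTF2 runs from first-line start to the end of second line. SAP Criterion 5 (mutation present) and Criterion 7 (minimum elapsed time) are both tied to the index start.

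**The concern.** Eligibility should be settled by what is known at time zero. Here two exclusions can be triggered by something that happens after the index EGFR-TKI has stopped, which is after the primary endpoint has occurred.

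Consider a patient whose first-line index afatinib fails with active brain metastases. On an any-line reading of exclusion 2, this patient is excluded if the next drug is an EGFR-TKI and retained if it is chemotherapy. Under the listed wording of exclusion 1, a patient treated in routine practice who later joins, say, an immunotherapy trial is also removed.

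Such removals take out observed failures and leave patients still on treatment untouched, so the Kaplan-Meier median for time on treatment rises. OS moves in opposite directions: exclusion 2 removes patients with a poor outlook, while exclusion 1 probably removes patients fit enough to enter a trial. TTF2 is also selected on, because the removal happens during its follow-up.

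Protocol 9.9 and 9.12 do not list either effect. Section 9.12 instead presents applying the exclusions to consecutive patients as protection against selection bias.

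**Working it through.** **Who is exposed (counting first- and second-line EGFR-TKI starts)**

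| Group | Exclusion 2 can act after index failure? | Exclusion 1 as listed can act after index failure? |
|---|---|---|
| Uncommon, first-line index, second-line EGFR-TKI | Yes, on the any-line reading | Yes |
| Uncommon, first-line index, other or no second line | No | Yes |
| Uncommon, second-line index | No; both starts are at or before the index | Yes |
| Sequencing (index is second-line osimertinib) | No; it can act after time zero (afatinib start) but not after the index has failed | Yes |

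**Size.** The plan has no figure to reproduce here: it gives no rate of second-line EGFR-TKI use, of active brain metastases at that point, or of later trial entry. Everything below is assumed.

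*Inputs.* All patients have a first-line index. Index duration is exponential with median 12 months. Follow-up is uniform on 12 to 60 months. Survival after index failure is exponential with median 12 months, replaced by 4 or 6 months with active brain metastases and by 18 or 24 months for trial entrants. Of those whose index fails, 25 to 40% start a second-line EGFR-TKI and 10 to 25% of these have active brain metastases; separately, 5 or 10% enter a later trial.

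*Share removed.* With rate ln2/12 per month, the probability that index failure is seen before data collection is 1 − (0.5 − 2⁻⁵) / ((ln2/12) × 48) = 1 − 0.469/2.773 = 0.831. Then:
- exclusion 2: 0.831 × 0.25 × 0.10 = 2.1%; 0.831 × 0.25 × 0.25 = 5.2%; 0.831 × 0.40 × 0.25 = 8.3%;
- exclusion 1: 0.831 × 0.05 = about 4%; 0.831 × 0.10 = 8.3%.

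*Kaplan-Meier OS medians (months), 400,000 simulated patients:*

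| Rule | Removed | Post-index median of those removed | All patients | After removal | Shift |
|---|---|---|---|---|---|
| Exclusion 2 | 2.1% | 4 | 28.72 | 29.12 | +0.40 |
| Exclusion 2 | 2.1% | 6 | 28.81 | 29.12 | +0.31 |
| Exclusion 2 | 5.2% | 4 | 28.29 | 29.29 | +1.00 |
| Exclusion 2 | 5.2% | 6 | 28.51 | 29.29 | +0.78 |
| Exclusion 2 | 8.3% | 4 | 27.85 | 29.44 | +1.59 |
| Exclusion 2 | 8.3% | 6 | 28.17 | 29.44 | +1.27 |
| Exclusion 1 | about 4% | 24 | 29.55 | 29.23 | −0.32 |
| Exclusion 1 | 8.3% | 18 | 29.67 | 29.46 | −0.21 |
| Exclusion 1 | 8.3% | 24 | 30.06 | 29.42 | −0.64 |

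The remaining combination (exclusion 1, about 4%, 18 months) gives about −0.1 in a larger run. Median time on treatment moves from 11.99 to between 12.07 and 12.31 months under exclusion 2, and by the same +0.1 to +0.3 under exclusion 1.

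*If early failures are removed more often.* The shift of 0.1 to 0.3 assumes removal is unrelated to how soon the index failed. With true medians of 10 or 12 months and follow-up uniform from 11.5 to 24 or 60 months, removing 2% of failures lengthens the median by 0.4 to 1.6%, and removing 5% by 1.0 to 4.0%. The upper ends have failures before the median three times as likely to be removed. At 10% of failures, a 12-month median and 60-month maximum follow-up (8.3% of the cohort), the median is 12.34 without that imbalance and 13.01 with it.

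*Dilution.* Second-line-index patients are not exposed to exclusion 2. Protocol 9.5 requires at least 50% treated with a first-line EGFR-TKI. If only half had a first-line index, the exclusion 2 shares would fall to 2.1% × 0.5 = 1.0% and 8.3% × 0.5 = 4.2%.

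**The case against.** **Exclusion 2 may already mean the index line.** It speaks of the start of EGFR-TKI therapy in a cohort that admits first- or second-line starts, so the parenthesis can mean whichever line held the studied drug. Inclusion 7 is equally unqualified, and the SAP resolves it to the index start. This stands: a reader might infer that the plan definitely applies exclusion 2 at every line, and the text does not settle that.

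**The SAP's brain-metastasis variable is not the eligibility check.** SAP chapter 3 defines "Patients with presence of brain metastases at start of EGFR therapy (either at first- or second-line"), which might be taken as proof of the any-line reading. It is a descriptive variable, covers any rather than active metastases, and is not part of Criterion 9. It lends support and no more. Any truncation of new brain sites in Table 8-UNC likewise depends on the any-line reading.

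**Exclusion 1 never mentions treatment line, and excluding trial treatment has a stated purpose.** Both true. But that purpose covers only trials of the studied drugs, and the operative list and Criterion 8 go further with no time limit. That mismatch exists on any reading.

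**The effect is small against sampling error.** Under the assumptions above with 250 patients, the expected 95% interval is about 4.2 months wide for median time on treatment and 7.5 for OS. A shift of 0.1 to 0.3 months is 2 to 7% of the former; the largest OS shift, 1.6, is about 21% of the latter and needs the worst combination of inputs. This stands as to size, but the bias does not shrink with more patients.

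**Conclusion.** The point holds for the uncommon cohort. Neither exclusion has a judgement date, although Criteria 5 and 7 do, so patients can be removed for events after the primary endpoint. For exclusion 2 this is conditional on the any-line reading and confined to first-line-index patients who start a second-line EGFR-TKI. A reader might extend it to the sequencing cohort or to second-line-index patients; the index definitions rule out exclusion 2 acting there after index failure. Exclusion 1 as listed is broader than its rationale in both cohorts.

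Direction is clear for time on treatment: both rules lengthen it, by about 0.1 to 0.3 months if 2 to 8% are removed without regard to failure time, and by more if early failures go preferentially. For OS, exclusion 2 adds about 0.3 to 1.6 months. Exclusion 1 subtracts about 0.1 to 0.6 if trial entrants live longer, as assumed. It should not be inferred that the two cancel, or that these are estimates of the actual bias: every rate is assumed. The effect on TTF2 was not quantified. Differences between EGFR-TKIs are possible but cannot be sized, and the plan's comparisons of them are descriptive only.

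**What to change.** - **Exclusion 2 and Criterion 9, uncommon cohort:** state that active brain metastases are judged at the start of the index EGFR-TKI.
- **Exclusion 1 and Criterion 8:** reconcile with the rationale by limiting them to the studied treatment given within an interventional trial (the index EGFR-TKI; in the sequencing cohort, afatinib or osimertinib). Leave the separate GioTag exclusion as it is.
- **Later-line trial participants:** keep them. Add sensitivity analyses of OS and TTF2 that leave them out or censor them at trial entry, noting that this censoring may be informative and that leaving them out brings back the selection.
- **Reporting:** give the number of patients excluded solely for post-index events, where known, and add the issue to Protocol 9.9 and 9.12.

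**Cost.** A wording amendment to the protocol and SAP, with the ethics and authority approvals that Protocol 10.1.1 requires. Sites would have to repeat some chart checks: Protocol 9.2.1 requires a log only of included patients, and the SAP's violation tables cover only patients entered in the eCRF, so those screened out may not be listed anywhere. Some trial treatment would then fall within OS and TTF2, which the sensitivity analyses address.
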